### **5.3 Inclusion of Women, Minorities and Children**

Both men and women and members of all races and ethnic groups are eligible for this study. Children are not eligible for this study because the safety and tolerability of the proposed administration schedule has not been determined in adults.

### **5.4 Withdrawal Criteria**

Protocol therapy will be discontinued at any time if any of the following situations occur:

1. Progressive disease (not including unconfirmed radiographic PD if Investigator opts to continue treatment as outlined in section [8.2.1](#)).
2. Adverse event.
  - The development of toxicity which, in the Investigator's judgment, precludes further therapy.
  - Unacceptable adverse event(s).
  - Intercurrent illness that prevents further administration of treatment.
3. Withdrawal by subject.
4. Lost to follow-up.
5. Non-compliance.
6. At the discretion of the Investigator/physician decision.

7. Death.
8. Pregnancy.
9. Study termination.

#### **5.4.1 Withdrawn Patients**

When a patient is removed from the study, the Investigator will clearly document the reason in the medical record and complete the appropriate case report form page describing the reason for discontinuation. In addition, every effort should be made to complete the appropriate assessments listed in Section [7.4](#).

Patients lost to follow-up will be withdrawn from the study. Patients will be declared “lost to follow-up” if the last contact date has exceeded two years, and/or the site has documented three attempts to contact the patient by telephone and/or certified letter to last known address.

#### **5.4.2 Replacement of Subjects**

Patients who discontinue due to toxicity (related to PTX-35) during the 4-week DLT window of observation of Cycle 1 and Cycle 2, or who do not receive all doses due to toxicity in Cycle 1 and Cycle 2, will not be replaced. Patients who discontinue or who do not receive at least two doses of PTX-35 for any reason other than toxicity during Cycle 1 and 2 will be replaced. Note, that all patients who receive PTX-35 will be included in assessment of DLT per Section [6.1.3](#).

### **5.5 Study Stopping Criteria**

If any of the following occur, administration of PTX-35 will be temporarily or permanently stopped, pending a review by the Safety Review Committee. During that time, no drug can be administered to any patient, until a decision is made.

- Any Death (other than progressive disease) that is at least possibly related to the study agent(s)
- Occurrence of two or more grade 4 events that are at least possibly related to the study agent(s)

Conditions that may warrant trial termination are listed in Section [4.6](#)

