#### DLT excludes:

- Hematological and non-hematological  $\leq$  Grade 2 unless considered non-acceptable.
- Other Grade 3 self-limited or medically controllable toxicities (e.g., fever without  $\geq$  Grade 3 neutropenia, lymphopenia, nausea, vomiting, diarrhea, fatigue). Note, such events are considered DLT if the abnormality leads to hospitalization or the abnormality persists for  $>72$  hours despite appropriate interventions (e.g., replacement therapy for electrolyte abnormalities, when indicated).
- Electrolyte disturbances that are managed to Grade 1 or less with supplemental therapy.

Any adverse event that is potentially related to PTX-35 and requires discontinuation of treatment should be considered a DLT. A DLT will be considered related to PTX-35 treatment unless there is a clear, well-documented relation to intercurrent illness or primary malignant disease. AEs that meet the above criteria but occur after the DLT evaluation period will not be defined as DLTs but will be reported as AEs/Serious Adverse Events (SAEs), as applicable, and will be reviewed across all cohorts during the study to help inform dose escalation decisions.

In case of suspicion of a DLT, the Investigator must inform the Medical Monitor/Sponsor immediately. The DLT will be confirmed by the Medical Monitor/Sponsor and a decision must be taken by the Sponsor regarding if an *ad hoc* SRC meeting is required.

Patients who discontinue therapy before completion of 2 cycles (DLT period) for other reasons than dose-limiting toxicity will be replaced. Patients who are tolerating PTX-35 will not have to discontinue study treatment prematurely due to the occurrence of DLTs in another patient in the same cohort, unless decided by the SRC.

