### **8.1.2.4 Serious Adverse Event (SAE)**

A serious adverse event is defined as any untoward medical occurrence that at any dose:

1. Results in death,
2. Is life-threatening (i.e., the patient was at risk of death at the time of the event. It does not refer to an event which hypothetically might have caused death if it was more severe),
3. Requires in-patient hospitalization or prolongation of existing hospitalization excluding that for pain management, disease staging/re-staging procedures, or catheter placement unless associated with other serious events,
4. Results in persistent or significant disability/incapacity, or
5. Is a congenital anomaly/birth defect.

Important medical events that may not result in death, be life-threatening, or require hospitalization may be considered serious adverse drug events when, based on appropriate medical judgment, they may jeopardize the patient and may require medical or surgical intervention to prevent one of the outcomes listed above.

Disease Progression, or death as a result of disease progression, **are not considered to be SAEs**. However, if the progression of the underlying disease is greater than what would normally be expected as part of the natural course of the disease under study for the patient, or if the Investigator considers that there was a causal relationship between treatment with study drug or protocol design/procedures and the disease progression, then it must be reported as an SAE.

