### **8.1.2.6 Reporting of Serious Adverse Events**

Adverse events classified as serious require expeditious handling and reporting to Sponsor or its designee to comply with regulatory requirements.

For any serious adverse event (SAE) that occurs while a patient is on-study; within 30 days of the last study drug administration, regardless of any opinion as to the relationship of the SAE to the study drug; or if any SAE that the Investigator feels is related to the study drug occurs later than 30 days after the last study drug administration, the Sponsor or its designee must be notified immediately (within 24 hours of becoming aware of the event).

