### **8.1.2.7 Safety Data Review**

#### ***8.1.2.7.1 Safety Review Committee***

A Safety Review Committee (SRC) comprised of at least three members – one Investigator, a representative from Pelican Therapeutics and the Medical Monitor will evaluate the data obtained at each dose level including a review of all adverse events (serious and non-serious adverse events) as they are reported by the study site. The SRC will recommend whether the dose should be escalated as per protocol, revised to a lower level or intermediate level, halted altogether or more patients are required at the same dose level to evaluate safety.

Ad-hoc SRC meetings may be called for by both the SRC and Sponsor any time during the study if DLTs are observed and/or new safety data warrants immediate action to the conduct of the trial (including events defined by the Study Stopping Criteria in Section [5.5](#)).

The conclusion of the SRC meeting will be documented in meeting minutes. The outcome of the SRC meeting will be communicated to all Investigators.

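### The trial-wide pause in 5.5 counts all related Grade 4 events, but those that are neither serious nor suspected DLTs have no timed report to the sponsor

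*Combined protocol and SAP*

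**What the plan says.** Section 5.5 (Study Stopping Criteria) has two triggers. One is "Any Death (other than progressive disease) that is at least possibly related to the study agent(s". The other is "Occurrence of two or more grade 4 events that are at least possibly related to the study agent(s". On their effect it says: "During that time, no drug can be administered to any patient, until a decision is made". Section 4.6 describes these events as calling for an immediate stop until the SRC has reviewed them.

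Two sections set fast notice from site to sponsor.

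- **Serious adverse events (SAEs), 8.1.2.6:** "the Sponsor or its designee must be notified immediately (within 24 hours of becoming aware of the event".
- **DLTs, 6.1.3:** "In case of suspicion of a DLT, the Investigator must inform the Medical Monitor/Sponsor immediately". DLTs exist only within Cycles 1 and 2. Events that meet the criteria but "occur after the DLT evaluation period will not be defined as DLTs but will be reported as AEs/Serious Adverse Events (SAEs), as applicable".

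For other adverse events, 8.1.2.1 requires an entry in the case report form (CRF) and source record. Section 12.1 asks that CRF data be submitted promptly but gives no number of days.

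On progression, 8.1.2.4 says that it is normally not an SAE, but that it must be reported as one "if the Investigator considers that there was a causal relationship between treatment with study drug or protocol design/procedures and the disease progression".

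**The concern.** A pause that rests on a trial-wide count works only as fast as the events reach whoever is counting. The Grade 4 trigger in 5.5 covers a wider set of events than the two fast routes do. For the events in between, the protocol sets no limit on the time from occurrence to sponsor awareness. Treatment is open-ended and more than one center is listed, so two such events can arise at different sites, late in treatment, without either site knowing of the other.

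This is a first-in-human study, and 2.6 states that no human safety data exist. Section 5.5 is its only automatic, event-defined pause for all patients. Individual dose holds protect the patient who has the event. The pause protects everyone else.

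A smaller question concerns deaths. The exception in 5.5 removes progression deaths from the trigger, while 8.1.2.4 recognizes that progression may be considered drug-related.

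**Working it through.** The plan states no figure on this point (9.8 says that no sample size calculation was made), so there is nothing to reproduce. The check traces each trigger to each reporting route.

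**1. What 5.5 counts.** Any Grade 4 event with attribution possible or definite (the categories in 8.1.2.2). There is no condition on seriousness, DLT status or time.

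**2. What is reported fast.** SAEs within 24 hours (8.1.2.6), and suspected DLTs immediately (6.1.3). The DLT window is Cycles 1 and 2: 2 × 14 = 28 days.

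**3. Whether a Grade 4 event can fall outside both.** Yes. The SAE criteria in 8.1.2.4 turn on outcome, hospitalization, actual risk of death or medical opinion, not on CTCAE grade. Section 6.1.3 itself applies Grade 4 to laboratory values (AST, ALT). Hematology and chemistry are drawn on Day 1 of every cycle, including Cycle 3 onward (Table 2, 7.3.4), and treatment has no fixed end (4.5). An asymptomatic, related Grade 4 laboratory value at Cycle 3 or later is therefore outside the DLT route, and outside the SAE route unless the Investigator classes it as serious.

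**4. Where that event goes.** To the CRF (8.1.2.1), with no deadline (12.1). The SRC does review non-serious events, but only once sites have reported them (8.1.2.7.1), so its review inherits the same undefined delay. Section 6.3 brings in the sponsor or SRC only if a patient with a DLT-equivalent toxicity is to continue at a lower dose level. No section names who keeps the running count for 5.5.

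**5. Inside the window.** The DLT exclusion for corrected electrolyte disturbances has no upper grade. A corrected, non-serious Grade 4 electrolyte event may therefore also lack an immediate report.

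**6. Deaths.** The death trigger already requires possible relatedness, so the progressive-disease exception changes the result only for a progression death considered related. Under 8.1.2.4 and 8.1.2.6 that death is an SAE and reaches the sponsor within 24 hours. Under 5.5 it does not start the automatic pause. The protocol does not say whether this is intended.

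**7. Illustration of size.** The only document input is n = 22 to 34 (9.8). Assumed: a proportion p of patients has one related Grade 4 event each, and a share s of these events has a fast route. Let X ~ Binomial(n, p) be all such events and Y ~ Binomial(n, p·s) those reported fast. Since Y ≥ 2 implies X ≥ 2,

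P(X ≥ 2 and Y < 2) = P(X ≥ 2) − P(Y ≥ 2).

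For n = 22, p = 0.05, s = 0.5:

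- P(X ≥ 2) = 1 − 0.95^22 − 22 × 0.05 × 0.95^21 = 0.302
- P(Y ≥ 2) = 1 − 0.975^22 − 22 × 0.025 × 0.975^21 = 0.104
- Difference = 0.198

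| n | p | P(X ≥ 2) | s = 0.25 | s = 0.50 | s = 0.75 |
|---|---|---|---|---|---|
| 22 | 5% | 30.2% | 27.1% | 19.8% | 10.3% |
| 34 | 5% | 51.2% | 44.5% | 30.4% | 14.6% |
| 22 | 10% | 66.1% | 55.7% | 35.9% | 16.2% |
| 34 | 10% | 86.7% | 65.9% | 35.5% | 13.2% |

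The last three columns give the chance that the trigger is met with fewer than two events reported fast. At p = 2%, P(X ≥ 2) is 7.1% (n = 22) or 14.8% (n = 34). These are not probabilities that the pause never fires. They are probabilities that its timing depends on the route with no deadline.

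**The case against.** The best defense is that the safety net is wider than the two fast routes. The SRC reviews non-serious events. DLT-type events after the window are reviewed across cohorts to inform escalation (6.1.3). The important-medical-event clause in 8.1.2.4 lets an Investigator class a Grade 4 laboratory value as serious. Sections 6.2 and 6.3 delay or stop dosing for the affected patient. All of this stands, and it narrows the gap. It does not close it: the reviews wait on untimed reporting, the seriousness clause is discretionary, and the dose holds do not reach other patients.

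A reader might infer more than the documents support.

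- **That the pause cannot work.** It can. Related non-progression deaths and serious Grade 4 events reach the sponsor within 24 hours, and suspected DLTs immediately.
- **That 5.5 conflicts with 8.1.2.7.1,** which says "Ad-hoc SRC meetings may be called for by both the SRC and Sponsor any time during the study". It does not. That sentence says who may convene a meeting, while 5.5 and 4.6 bar dosing until the SRC has reviewed. If no meeting is held, the stop continues.
- **That 5.5 contradicts 8.1.2.4 on progression deaths.** One section governs stopping and the other reporting, and the SAE report still allows an ad hoc SRC meeting, which can recommend a halt.
- **That regulatory T-cell expansion makes drug-driven progression likely.** Sections 2.1.3 and 2.4.1 report expansion in the mouse spleen but none in the tumor, together with anti-tumor effects.
- **That a number of excess doses can be stated.** The documents give neither the reporting delay nor the number on treatment, and patients with the events would themselves be held under 6.2 or 6.3.

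**Conclusion.** The gap is real and narrow. Related Grade 4 events that are neither SAEs nor suspected DLTs count toward the trial-wide pause but have no timed report, so the pause may fire late. With 14-day cycles, each 14 days of delay spans one scheduled dose for every patient still on treatment and not individually held.

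How often this would matter cannot be derived from the documents. Over the assumed rates of 5% and 10% and fast-route shares of 25% to 75%, the chance that the trigger is met with fewer than two events reported fast runs from 10.3% to 65.9%. That range rests wholly on the assumptions, including one event per patient and the same rate at every dose level. It shows that the gap is not negligible; it is not an estimate.

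The death exception is a secondary point: a difference in scope between two sections that the protocol leaves unexplained.

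**What to change.** 1. In 8.1.2.6, extend the existing 24-hour notification to every Grade 4 event at least possibly related to study agent, whether or not it is serious and at any time on study. This also covers the corrected electrolyte case inside the DLT window.
2. State that the Medical Monitor keeps the running count across sites that 5.5 needs. Grade and attribution are already assessed for each event (8.1.2.1, 8.1.2.2), so no new data item is required.
3. Separately, the sponsor should reconcile the progressive-disease exception in 5.5 with 8.1.2.4 and state how a progression death considered related to study drug is handled. No answer is proposed here, and no stopping threshold is changed.

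The cost is a wording amendment that uses the notification channel already in place. The downside is a few extra expedited reports, mostly for asymptomatic laboratory values.

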## 6.0 TREATMENT OF PATIENTS

### 6.1 Investigational Product Preparation and Administration

#### 6.1.1 Drug Products

##### 6.1.1.1 PTX-35

PTX-35 is a humanized, affinity matured, IgG2 monoclonal antibody and is a functional agonist of human TNFRSF25, a member of the TNF-receptor superfamily that is expressed preferentially by activated and antigen-experienced T lymphocytes.

The drug substance is manufactured by KBI Biopharma (Durham, NC) and formulated in 20 mM histidine (pH 6.5) and 250 mM sorbitol at a target of 25 mg/mL and stored frozen at -80°C in PETG bottles.

The final drug product is reformulated and filled at Integrity Bio (Camarillo, CA) at a final concentration of 10 mg/mL in 20 mM histidine (pH 6.0), 250 mM sorbitol and 0.01% polysorbate 80 and stored at 2–8°C.

PTX-35 will be administered via intravenous infusion according to the dose levels in the dose escalation scheme (Section [6.1.2](#)) on Day 1 of each cycle. The dose will be calculated using the weight obtained during Screening. The weight obtained at each dosing visit is to be reviewed prior to dispensing IP. If the patient's weight changes by >10% during the course of the study, the drug dose should be recalculated. Recalculation of drug dose on each treatment day regardless of percentage of body weight change is also allowed, if required per institutional dosing policy. The dosing solution should include additional volume to account for dose losses due to administration set priming. PTX-35 should be diluted with 0.9% sodium chloride for injection under aseptic conditions to the appropriate concentration according [Table 1: PTX-35 Dose Levels](#). Dose levels 1 through 3 will be administered at a concentration of 1 mg/mL, and dose levels 4 through 7 will be administered at a concentration of 5 mg/mL. Diluted Investigational Product should be infused with a MedFusion 3500 syringe pump (or equivalent) with compatible polypropylene syringe connected to Smith's Medical FS116 60" PVC tubing with 0.22 micron in-line filter and 0.7 mL priming volume. [Note that the total priming volume to be used during administration will be 1.0 mL to ensure filter saturation.] The rate of infusion should be approximately 1 mL per minute. Please refer to the study Investigational Product Manual for full administration details.

Each patient must remain in clinic for a 6-hour safety observation period after the first cycle of PTX-35 infusion. Afterwards, the Investigator may reduce the observation period to 2 hours for the remaining cycles according to the following criteria:

- Absence of any significant safety concerns following a complete review of all clinical and laboratory data for all treated subjects at the given dose level and the preceding dose levels,
- Absence of any late-onset (>2 hours post dose) infusion-related reactions or IRR symptoms that continue beyond 2 hours post-dose, and lack of any severe or serious IRRs,

#### **6.1.1.2 TENIVAC Vaccine**

TENIVAC vaccine is a suspension available in 0.5 mL single-dose for injection. TENIVAC vaccine is a sterile isotonic suspension of tetanus and diphtheria toxoids adsorbed on aluminum phosphate. Each 0.5 mL dose of TENIVAC vaccine contains the following active ingredients: Tetanus Toxoid 5 Lf (flocculation units) and Diphtheria Toxoid 2 Lf. Other ingredients per 0.5 mL dose include 1.5 mg of aluminum phosphate (0.33 mg of aluminum) as the adjuvant and ≤5.0 mcg of residual formaldehyde.

TENIVAC will be administered via intramuscular injection on Day 1 of Cycle 1 only and will be administered per the current product package insert.

If any serious adverse reaction occurs these may be treated per institutional practice, as noted in Section [6.4 Concomitant Treatment](#).

#### **6.1.2 Dose Escalation Scheme**

Escalating doses of PTX-35 will be administered to patients via intravenous infusion on Day 1 of each cycle.

Upon completion of two cycles (4 weeks), in the absence of disease progression or unacceptable toxicity, patients may continue to be treated with PTX-35 at the same dose and schedule until disease progression, death, and patient withdrawal of consent, Investigator's decision to remove patient, or intolerable toxicity, whichever occurs first. At the discretion of the Investigator, treatment with PTX-35 may continue beyond initial evidence of radiological progression as per Section [8.2.1](#).

Seven escalating dose levels of PTX-35 will be explored using a traditional 3+3 design based on DLTs (dose-limiting toxicities) until MTD (maximum tolerated dose) or optimal immunological dose (OID) is established. The starting dose of PTX-35 is based on the MABEL for Treg activity (considered the most sensitive of PTX-35 pharmacodynamic markers) obtained from dose-ranging studies conducted in non-clinical animal models. PTX-35 will be administered to patients intravenously on Day 1 of each cycle. The length of each cycle is

14 days, and the DLT observation period includes the safety data obtained from the first two treatment cycles (4 weeks).

**Table 1: PTX-35 Dose Levels**

Dose level*	PTX-35 dose (mg/kg)	PTX-35 Concentration (mg/mL)	PTX-35 Dose (mL/kg)	Number of patients
1	0.01 mg/kg	1 mg/mL	0.01 mL/kg	3-6
2	0.03 mg/kg	1 mg/mL	0.03 mL/kg	3-6
3	0.10 mg/kg	1 mg/mL	0.10 mL/kg	3-6
4	0.30 mg/kg	5 mg/mL	0.06 mL/kg	3-6
5	1.0 mg/kg	5 mg/mL	0.20 mL/kg	3-6
6	3.0 mg/kg	5 mg/mL	0.60 mL/kg	3-6
7	10 mg/kg	5 mg/mL	2.0 mL/kg	3-6

*\*Dose levels 1 through 3 will be administered at a concentration of 1 mg/mL, and dose levels 4 through 7 will be administered at a concentration of 5 mg/mL.*

At each dose level, 3 patients will be enrolled, with a minimum waiting period of one week after treatment initiation of the first patient only. The remaining subjects in the dose level will be treated with no stagger. After all 3 patients in a dose level have received the second dose of PTX-35 and completed the DLT observation period, the Safety Review Committee (SRC) will review the safety data to make a dose escalation decision. If none of these 3 patients experiences a DLT, dose escalation may proceed. If 1 of these 3 patients experiences a DLT, the dose level will be expanded to at least 6 patients at the same dose level. If  $\leq 1$  out of 6 patients experiences a DLT, then the SRC may recommend dose escalation to the next dose level. If a DLT occurs in 2 or more patients in a particular dose level, the maximum tolerated dose (MTD) has been exceeded and dose escalation will cease. Up to 3 additional patients will be enrolled at the next lowest dose if only 3 patients were treated at that dose level, to confirm safety of that dose.

The conduct and completion of each subsequent dose cohort will follow in similar fashion until the MTD is established. Note that if the optimal immunological dose (OID), or observed plateau of Treg activity, is determined prior to MTD, further dose escalation may be discontinued by decision of the SRC.

Visits and study examinations will be performed per [Table 2: Schedule of Assessments](#). Safety will be assessed by frequency of treatment-emergent adverse events (TEAEs), evaluation of clinical laboratory parameters (hematology and biochemistry), weight, vital signs, electrocardiogram (ECG), performance status, and physical exam findings. NCI CTCAE version 5.0 will be used to grade all toxicities.

A post-treatment safety visit will be conducted approximately 30 days following the last dose of PTX-35. Response to treatment will be assessed according to RECIST 1.1 with planned evaluation performed every 8 weeks ( $\pm 1$  week) from the start of treatment (C1D1).

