### Study Overview:

This is an open-label, single arm, first-in-human, Phase I study of intravenous administration of PTX-35 to patients with advanced solid tumors refractory to, or ineligible for, or who refuse available SOC.

Patients who meet the eligibility criteria will be enrolled to receive intravenous PTX-35 every two weeks as well as a single intramuscular injection of TENIVAC vaccine (tetanus and diphtheria toxoids adsorbed) on Day 1 of Cycle 1. Upon completion of two cycles of PTX-35, in the absence of disease progression or unacceptable toxicity, patients may continue to be treated with PTX-35 at the same dose and schedule until disease progression, death, and patient withdrawal of consent, Investigator's decision to remove patient, or intolerable toxicity, whichever occurs first.

Seven escalating dose levels of PTX-35 will be explored using a traditional 3+3 design based on dose-limiting toxicities (DLTs) until optimal immunological dose (OID) or maximum tolerated dose (MTD) is established. The starting dose of PTX-35 is based on the MABEL for Treg activity (considered the most sensitive of PTX-35 pharmacodynamic markers) obtained from dose-ranging studies conducted in non-clinical animal models. PTX-35 will be administered to patients intravenously on Day 1 of each cycle. The length of each cycle is 14 days, and the DLT observation period includes the safety data obtained from the first two treatment cycles (4 weeks).

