#### PTX-35 Dose Levels

Dose level*	PTX-35 dose (mg/kg)	PTX-35 Concentration (mg/mL)	PTX-35 Dose (mL/kg)	Number of patients
1	0.01 mg/kg	1 mg/mL	0.01 mL/kg	3-6
2	0.03 mg/kg	1 mg/mL	0.03 mL/kg	3-6
3	0.10 mg/kg	1 mg/mL	0.10 mL/kg	3-6
4	0.30 mg/kg	5 mg/mL	0.06 mL/kg	3-6
5	1.0 mg/kg	5 mg/mL	0.20 mL/kg	3-6
6	3.0 mg/kg	5 mg/mL	0.60 mL/kg	3-6
7	10 mg/kg	5 mg/mL	2.0 mL/kg	3-6

\*Dose levels 1 through 3 will be administered at a concentration of 1 mg/mL, and dose levels 4 through 7 will be administered at a concentration of 5 mg/mL.

At each dose level, 3 patients will be enrolled initially, with treatment initiation staggered by one week after the first patient only. After all 3 patients in a dose level have received the second dose of PTX-35 and completed the DLT observation period, the Safety Review Committee (SRC) will review the safety data to make a dose escalation decision. If none of these 3 patients experiences a DLT, dose escalation may proceed. If 1 of these 3 patients experiences a DLT, the dose level will be expanded to at least 6 patients at the same dose level. If  $\leq 1$  out of 6 patients experiences a DLT, then the SRC may recommend dose escalation to the next dose level. If a DLT occurs in 2 or more patients in a particular dose level, the maximum tolerated dose (MTD) has been exceeded and dose escalation will cease. Up to 3 additional patients will be enrolled at the next lowest dose if only 3 patients were treated at that dose level, to confirm safety of that dose.

The conduct and completion of each subsequent dose cohort will follow in similar fashion until the MTD is established. Note that if the optimal immunological dose (OID), or observed plateau of Treg activity, is determined prior to MTD, further dose escalation may be discontinued by decision of the SRC.

Visits and study examinations will be performed per [Table 2: Schedule of Assessments](#). Safety will be assessed by frequency of treatment-emergent adverse events (TEAEs), evaluation of clinical laboratory parameters (hematology, and biochemistry), weight, vital signs, electrocardiogram (ECG), performance status, and physical exam findings. NCI CTCAE version 5.0 will be used to grade all toxicities.

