### **7.3.2 Days 2, 4, 7, and 10 of Cycle 1 and Cycle 2**

- Blood sample for pharmacokinetics at the following post-dose time points:  
Day 2 - 24hr ( $\pm 2$ hr), Day 4 – 72hr ( $\pm 2$ hr), Day 7 – 144hr ( $\pm 2$ hr) and Day 10 – 216hr ( $\pm 2$ hr)
- Blood sample for immunological effect (Day 7 only)
- Concomitant medications review
- Adverse event assessment

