### **7.3.3 Day 1 of Cycle 2 (+ 2 days)**

- Physical exam
- Weight
- Vital signs (blood pressure, heart rate, respiratory rate, and temperature): pre-dose; 30 min ( $\pm 5$  min) and 1hr ( $\pm 5$  min) after end of PTX-35 infusion
- ECG (a standard 12-lead ECG in triplicate (approximately 2 to 5 minutes apart) taken while patient is in a semi-recumbent position
- ECOG Performance status
- Blood draw for hematology
- Blood draw for serum chemistry tests
- Blood sample for pharmacokinetics at 4 timepoints: pre-dose; 30min ( $\pm 5$  min), 2hr ( $\pm 5$  min) and 4hr ( $\pm 5$  min) after end of PTX-35 infusion
- Blood sample for cytokines at 2 time points: pre-dose and 2hr ( $\pm 5$  min) after end of PTX-35 infusion
- Blood sample for anti-therapeutic antibodies (ATA) and anti-TENIVAC antibody titer (pre-dose)
- Blood sample for immunological effect (pre-dose)
- PTX-35 administration and observation period
- Concomitant medications review
- Adverse event assessment

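### At the minimum one-week stagger, patients 2 and 3 of a dose level may be dosed 7 to 9 days before the first patient's first scheduled post-dose hematology and chemistry

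*Combined protocol and SAP*

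**What the plan says.** **Stagger.** Section 6.1.2 (text under Table 1) enrols three patients at each level "with a minimum waiting period of one week after treatment initiation of the first patient only". It continues: "The remaining subjects in the dose level will be treated with no stagger". The synopsis says the same: "with treatment initiation staggered by one week after the first patient only".

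**Laboratory schedule.** Table 2 and Sections 7.2 to 7.3.3 place hematology and serum chemistry at pre-treatment, Cycle 1 Day 1 and Cycle 2 Day 1. Section 7.3.1 and Table 2 footnote c let the Cycle 1 Day 1 tests be done up to 3 days earlier. Section 7.3.2 covers Days 2, 4, 7 and 10. It lists a PK sample, concomitant medications, adverse event assessment and "Blood sample for immunological effect (Day 7 only"), but no hematology or chemistry. "Blood draw for hematology" and the chemistry draw next appear in Section 7.3.3, at Cycle 2 Day 1, which has a window of +2 days. On cycle length the synopsis states: "The length of each cycle is 14 days".

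**What counts as safety data.** Section 6.1.2 names hematology and biochemistry among the means of assessing safety. Section 9.3 lists cytokines with them as laboratory evaluations. Section 6.1.3 includes DLT criteria defined by blood results: hematological toxicity of Grade 3 or above, total bilirubin, AST and ALT.

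**The concern.** A wait after the first patient of a level is useful to the next two only to the extent that information about that patient accrues during it. Cytopenia and changes in transaminases or bilirubin can be silent, and they are among the events that Section 6.1.3 may count as DLTs. At the minimum interval the wait can end with no scheduled post-dose measurement of any of them. No section provides for a routine review of the first patient's data before patients 2 and 3 start. The escalation review in Section 6.1.2 comes only after all three have completed the DLT period.

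The plan does link laboratory review to a safeguard elsewhere. Section 6.1.1.1 allows a shorter post-infusion observation period only after clinical and laboratory data at that level and the preceding levels have been reviewed. The stagger has no corresponding statement. At stake is the first exposure of two patients per level in a trial for which Section 2.6 reports no prior human data.

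**Working it through.** This is calendar arithmetic. Section 9.8 gives no sample size calculation that would bear on it.

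**1. Day numbering.** Section 7.3.2 pairs study days with hours after dosing. With hour = (day − 1) × 24:
- Day 2: 1 × 24 = 24 h
- Day 4: 3 × 24 = 72 h
- Day 7: 6 × 24 = 144 h
- Day 10: 9 × 24 = 216 h

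All four match the plan's own figures, so the same rule can place the stagger on the visit schedule.

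**2. Earliest end of the stagger** (Section 6.1.2, one week). 7 × 24 = 168 h; 168/24 + 1 = Day 8.

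**3. First scheduled post-dose hematology and chemistry** (14-day cycle; Section 7.3.3, +2 days). 14 × 24 = 336 h, which is Day 15. With the window, 336 + 48 = 384 h, which is Day 17.

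**4. Gap.** (336 − 168)/24 = 7 days; (384 − 168)/24 = 9 days.

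**5. First-patient visits completed by 168 h.** Days 2, 4 and 7 (24, 72 and 144 h). Day 10, at 216 h, falls 48 h after the earliest release and does not count.

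**6. First-patient data scheduled by 168 h.**

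| Item | When | Source |
|---|---|---|
| Observation in clinic | 6 h after the first infusion | 6.1.1.1; Table 2 note j |
| Vital signs | 30 min and 1 h after infusion | 7.3.1; Table 2 note d |
| Cytokines | 2 h after infusion | 7.3.1; 8.7 |
| Adverse event assessment | Days 1, 2, 4, 7 | 7.3.1; 7.3.2 |
| PK | Days 1, 2, 4, 7 | 7.3.1; 7.3.2 |
| Immunophenotyping | Day 7 | 7.3.2; 8.4 |
| Hematology, chemistry | none post-dose | Table 2; 7.3.1 to 7.3.3 |

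Neither Section 7.3.1 nor Table 2 labels the Cycle 1 Day 1 hematology and chemistry as pre-dose. Treating them as baseline is an inference from the 3-day allowance.

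**7. Patients affected.** Two per initial cohort of three; 2 × 7 levels = 14 at most. Patients 4 to 6 are not counted, because expansion follows review of the first three.

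**8. Effect of a Day 7 panel.** A draw at 144 h falls 168 − 144 = 24 h before the earliest release. The documents state no laboratory turnaround, so whether a result would be in hand by Day 8 is an assumption.

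**The case against.** The strongest answer is that this is a choice about monitoring, not an error. No two sections contradict each other, and the documents never say that the stagger is meant for laboratory review. That stands, and is why the point is put as an improvement and a request to reconcile.

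Four stronger inferences are tempting, and the documents do not support them:

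- **That patients 2 and 3 are dosed with no laboratory safety data from the first patient.** A cytokine sample is scheduled 2 h after the first infusion, and Section 9.3 counts cytokines as a laboratory evaluation. Cytokines do not show cytopenia or liver change, and no turnaround is stated, but the absence is specific to hematology and chemistry.
- **That the week can reveal symptoms only, or is the sole safeguard.** Vital signs and observation are scheduled. Suspected DLTs must be notified at once (Section 6.1.3), the Safety Review Committee reviews adverse events as they are reported (Section 8.1.2.7.1), and Section 5.5 can halt all dosing. None of these supplies a blood count or chemistry result.
- **That the early dosing will happen.** One week is a minimum. Slower enrolment could pass Day 15, and unscheduled tests remain possible if clinically indicated.
- **That a Day 7 panel would settle laboratory DLTs.** Under the hepatic criterion, Grade 3 AST or ALT must last more than 7 consecutive days, as must bilirubin of 2 to 3 × ULN. Controllable Grade 3 events such as lymphopenia are excluded unless they persist beyond 72 h or lead to hospitalization. One panel cannot establish duration. It could show other qualifying events, such as Grade 4 transaminases.

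Context also favors the sponsor. From level 2 upward, the first patient starts only after review of the level below, whose completed data include Cycle 2 Day 1 laboratory results. Section 2.6 expects mainly infusion, immune-related and cytokine reactions. Section 2.4.2 reports no clinical chemistry changes in monkeys. This lowers the likely risk but does not remove the gap at the new dose. The explicit statement of unchanged hematology is for mice, in which Section 2.4.1 says the human antibody lacks biological activity. The monkey summaries do not list hematology among unaffected parameters, though the Investigator's Brochure may say more.

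**Conclusion.** The point holds in this limited form: at the minimum interval the stagger can end on Day 8, 7 to 9 days before the first patient's first scheduled post-dose hematology and chemistry. It can affect up to 2 patients in each initial cohort. The figure of 14 is an upper bound that requires all seven levels to open and every cohort to enrol before the first patient's Cycle 2 Day 1 results.

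The conclusion assumes that the Cycle 1 Day 1 draw serves as baseline, that Cycle 2 starts on schedule, and that no unscheduled tests are done. It does not show that the first patient goes unmonitored or that the stagger length is wrong. It shows that two of the laboratory measures on which the plan says it relies are not scheduled within the interval the plan requires.

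**What to change.** - **Table 2 and Section 7.3.2:** add the existing hematology and serum chemistry panels (footnotes g and h) at the Cycle 1 Day 7 visit. Do this for all patients. If only the first patient of each level were tested, laboratory DLTs would be ascertained unequally within a cohort of three.
- **Section 6.1.2 and synopsis:** the sponsor should reconcile the stagger with the laboratory schedule, and state whether dosing patients 2 and 3 before any post-dose hematology or chemistry from the first patient is intended. The stagger length, any release condition and the response to an abnormal result are for the clinical team.

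**Cost.** About 5 + 5 = 10 mL of blood per patient, using the volumes in footnotes g and h, plus local laboratory cost. No new visit or venepuncture is needed: Day 7 already has a PK sample of about 1 mL (Section 8.3) and an immunophenotyping sample of about 23 mL (Section 8.4). At the stated target of 22 to 34 patients, this is 22 to 34 additional pairs of panels.
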